# **1** Summary of Trial Design

Title	Pilot evaluation of a personalised, prevention mHealth partner, SYD, and its impact on Quality of Life of NHS staff					
Short Title/acronym	SYD (See Yourself Differently) for NHS					
IRAS number	294071					
Sponsor name & reference	Southern Health NHS Foundation Trust					
Funder name & reference	iamYiam					
Design	Randomised Controlled Trial and Controlled Before and After Study					
Overall aim	To quantify the change in Quality of Life (QOL) following an intervention with SYD, a personalised preventive mHealth partner. Measures of mental health (stress, anxiety and depression) will also be tracked as a way to assess the wellbeing potential of this non-clinical intervention.					
Primary endpoint	
 
Determine the impact of SYD on Quality of Life of NHS Staff over 3 months, as measured through Generic and Anxiety Specific Quality of Life instruments:
 
1. EuroQoL EQ-5D-5L (Health-related QOL)
 
2. WHO Quality of Life-BREF (WHOQOL-BREF) survey (Global QOL)
 
					
Secondary endpoints	
 
Determine the efficacy of SYD in reducing levels of stress, anxiety and depression, as measured through the Perceived Stress Scale (PSS-4) and Hospital Anxiety and Depression Scale (HADS).
 
Determine user satisfaction and engagement with SYD
 
Determine the persistence of primary endpoint changes over 6-month time frame
 
					
Target accrual	500 participants randomised 1:1 to Control Group (=250) and Intervention Group (=250).					
Inclusion criteria	
 
Active NHS staff with an NHS email address which can be used for this study
 
Age ≥ 18 years
 
Own a personal smartphone device (iOS or Android-based) which can be used for this study
 
Sufficient English language ability to familiarise themselves with and engage with SYD and study assessments
 
Hospital Anxiety and Depression Scale (HADS) test score between 8 and 14 inclusive, indicating mild to moderate anxiety or depressive symptoms
 
Provision of informed consent
 
					
Exclusion criteria	
 
Unwilling or unable to participate
 
Any other concurrent psychological interventions
 
Concurrent participation in an interventional clinical trial
 
Considered clinically extremely vulnerable from COVID-19 https://www.gov.uk/government/publications/guidance-on-shielding- and-protecting-extremely-vulnerable-persons-from-covid-19/guidance- on-shielding-and-protecting-extremely-vulnerable-persons-from-covid- 19)
 
					

Title: Pilo	Title: Pilot evaluation of a personalised, prevention mHealth partner, SYD, and its impact on Quality of Life of NHS staff							
Authors	[name], [name], [name], [name], [name]	Ver.	2.0	Date Authorised	13/04/2022	Page 5 of 24		

Anticipated duration of recruitment	Approximately 12 months
Duration of trial	Approximately 22 months. The start of the trial is expected to be 1 st June 2021 and the end of trial by 31 st March 2022.
Definition of end of trial	The study end date is deemed to be the date which Health Research Authority is notified of the end of study.

Title: Pilot	Title: Pilot evaluation of a personalised, prevention mHealth partner, SYD, and its impact on Quality of Life of NHS staff							
Authors	[name], [name], [name], [name], [name]	Ver.	2.0	Date Authorised	13/04/2022	Page 6 of 24		

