#### Participants:

NHS staff, 18 years and over, who took part in the 'Psychological impact of the Coronavirus (COVID-19) pandemic and experience: An international survey' study (PIoC19 study; IRAS Project ID 282858; REC reference 20/HRA/1934), and provided informed consent to be contacted for future versions of the study ( $n \approx 3500$ ), will be invited to participate in the 'SYD for NHS' trial via email. Once this pool of potential participants is given the opportunity to participate, then the study will be offered to all NHS organisations who may wish to participate in the trial as Participant Identification Centres (PIC). PIC sites will be provided with an open link of the study website to share with their current staff.

Any interested potential participants will be directed to the study website and asked to familiarise themselves with the information provided in the Patient Information Sheet. Those participants who are interested to take part in the study will be asked to complete questions to confirm eligibility, following which they will be asked to consent to undertake a Hospital Anxiety and Depression Scale (HADS) test. Optional consent to be contacted for future ethically approved research in the field of mental health and digital health technologies will be sought. Potential participants who score between 8-14 inclusive will be eligible, as these scores indicate individuals most likely to benefit from interventions of wellbeing like SYD and to be considered safe as higher scores may indicate depression/anxiety levels needing formal psychological evaluation. Participants with HADS scores 15 and over will be advised that they might need to contact their GP for further support. Individuals with low levels of anxiety often do not engage well with wellbeing measures (Singer et al. 2009).

Following confirmation of informed consent, and confirmed eligibility from the screening questionnaire, participants will be randomised 1:1 to one of two groups: Control Group and Intervention Group. People considered clinically extremely vulnerable for COVID-19, are excluded to avoid conflict with government advice. (https://www.gov.uk/government/publications/guidance-on-shielding-and-protecting-extremely-vulnerable-persons-from-covid-19/guidance-on-shielding-and-protecting-extremely-vulnerable-persons-from-covid-19)

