### 3.9 Statistical analysis and sample size calculation

Approximately 3,500 NHS staff, 18 years and over, who took part in the PIoC19 study, and provided consent to be contacted will be invited to join the SYD for NHS trial.

We estimate that ~800 NHS staff will be interested and eligible to participate. As it is currently not known how many participants are likely to interact sufficiently with SYD and provide sufficient trial data, we have assumed that up to 800 participants will have to be randomised to achieve a target of 500 evaluable participants, 250 in each group. Data on all randomised participants will be evaluated and the drop-out rate in the intervention group will be determined.

As this is a pilot study to evaluate the impact of SYD, and not a superiority trial, we have estimated 500 patients being available to have reasonable confidence intervals of any changes in quality of life scales, if available. A previous study of the eBalance app showed significant lifestyle changes within 14 weeks in 85 participants with only 56 participants using the app (Safran Naimark, 2015).

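### The summary sets target accrual at 500 randomised, while Section 3.9 makes the same 500 the evaluable number and allows for up to 800 randomised to reach it

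*Protocol*

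**What the plan says.** The target accrual row in Protocol Section 1 (Summary of Trial Design) reads "500 participants randomised 1:1 to Control Group (=250) and Intervention Group (=250"). The count is of participants randomised.

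Protocol Section 3.9 attaches the same figures to a different quantity: "we have assumed that up to 800 participants will have to be randomised to achieve a target of 500 evaluable participants, 250 in each group". The reason it gives for the allowance is that "it is currently not known how many participants are likely to interact sufficiently with SYD and provide sufficient trial data".

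Section 3.9 rests the size on precision, not power. It describes the work with the words "As this is a pilot study to evaluate the impact of SYD, and not a superiority trial", and says "we have estimated 500 patients being available to have reasonable confidence intervals of any changes in quality of life scales". It gives no interval width, standard deviation, significance level, power or loss rate. It adds one earlier app study of 85 participants as context.

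Section 3.5 (Participants) confirms equal allocation: "participants will be randomised 1:1 to one of two groups: Control Group and Intervention Group".

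**The concern.** One pair of numbers, 500 in total and 250 per group, is a randomised count in the summary and an evaluable count in the sample size section. The gap between the two readings is up to 800 − 500 = 300 people. Section 3.9 itself separates randomised from evaluable and expects some participants not to provide sufficient data, so the two readings cannot both be the plan.

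The 500 evaluable participants are the protocol's stated basis for its precision. Someone working from the summary alone would treat 500 randomised as the target reached, and the trial would then fall short of the number on which the size was justified. The discrepancy also affects how many staff are approached, consented and randomised.

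**Working it through.** **Inputs.**
- Section 1: 500 randomised, 250 per group.
- Section 3.9: up to 800 randomised for 500 evaluable, 250 per group.
- Section 3.5: 1:1 allocation.
- Assumed here, because the protocol gives none: a two-sided 95% interval, an unadjusted comparison of two means at one time point, results in standard deviation (SD) units, and equal loss in the two groups.

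**Step 1. The plan's own figure.** The 500 cannot be derived, since no width, SD or loss rate is stated. The step from 500 to 800 can only be checked for internal consistency. The implied maximum loss is 1 − 500/800 = 0.375. Working back, 500/(1 − 0.375) = 800, and 250/(1 − 0.375) = 400 per group. Section 3.9 is therefore consistent with itself at a loss of up to 37.5%. Because the text says up to 800, this is a ceiling and not an expected rate.

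**Step 2. What the summary's 500 randomised would yield.** Evaluable number = 500 × (1 − loss). With n evaluable per group, half-width = 1.96 × √(2/n). Widening relative to 250 per group = √(1/(1 − loss)).

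| Loss | Evaluable from 500 randomised | Per group | Half-width (SD) | Widening | Randomised needed for 500 evaluable |
|---|---|---|---|---|---|
| 0% | 500 | 250 | 0.175 | none | 500 |
| 10% | 450 | 225 | 0.185 | 5% | 556 |
| 20% | 400 | 200 | 0.196 | 12% | 625 |
| 30% | 350 | 175 | 0.210 | 20% | 715 |
| 37.5% | about 312 | about 156 | 0.222 | 26% | 800 |

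For example, 1.96 × √(2/250) = 0.175, 1.96 × √(2/156) = 0.222, and √(1/0.625) = 1.265.

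**Step 3. Reading the table.** Only the zero-loss row makes the summary and Section 3.9 agree.

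**Step 4. Sensitivity to equal loss.** Equal loss follows Section 3.9's own figures (400 to 250 in each group). If the 37.5% loss fell on the intervention group only, the groups would be 250 and 500 × 0.5 × 0.625 = 156. The half-width would be 1.96 × √(1/250 + 1/156) = 0.200, about 14% wider than 0.175. The shortfall would be smaller but would remain.

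**The case against.** The strongest reply is that this is a labelling slip. Section 3.9 is the sample size section, the summary repeats its target with the wrong noun, and no power, test or decision rule changes. That is fair as a description of the cause. It does not make the two statements agree, and the summary is where many readers look for the accrual figure.

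A second reply is that participants who are not evaluable do not simply leave the analysis. Section 3.9 says data on everyone randomised will be evaluated, Section 9 keeps data up to withdrawal, and Section 10.1 plans mixed models, adjustment for baseline characteristics and imputation where plausible. Partial data from Months 0 to 3 would recover some precision. In addition, being evaluable depends partly on using SYD, and controls are not invited to use it until Month 4, so that component cannot reduce the control group at Month 3. These points stand. They soften the half-widths above but do not reconcile the counts.

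Three stronger readings are tempting, and the documents do not support them.
- A reader might infer that 500 randomised would give about 312 evaluable and intervals 26% wider. Those figures are the worst case within the protocol's allowance; at 10% to 20% loss the widening is about 5% to 12%. Nor can it be shown that a planned precision is missed, because the protocol calls its intervals reasonable without a number.
- A reader might infer that the sponsor cannot tell when recruitment is complete. Section 8 sets a recruitment end date of 15 April 2022, two days after this version was authorised on 13 April 2022.
- A reader might infer that the roughly 800 interested and eligible staff in the first pool would all have to be randomised. Sections 3.5 and 4 then open the study to other NHS organisations, so recruitment is not confined to that pool.

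**Conclusion.** The contradiction is real and concerns the trial's headline sample size: 500 is the number randomised in Section 1 and the number evaluable in Section 3.9. What is demonstrably missed at 500 randomised is the 500 evaluable, under any loss above zero. The shortfall runs from 0 to about 188 participants (500 − 312), depending on a loss rate that the protocol says is unknown.

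The effect on precision is indicative. It assumes a 95% level, an unadjusted comparison at a single time point and equal loss in the two groups. On those assumptions the half-width lies between 0.175 and about 0.222 SD, with 26% as the upper limit of the widening. The planned models would probably narrow the gap.

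**What to change.** Change the target accrual row in Section 1 to match Section 3.9: up to 800 participants randomised 1:1 (up to about 400 per group) to achieve 500 evaluable (250 per group).

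If recruitment in fact closes near 500 randomised, amend Section 3.9 instead. It should say that 500 is the number randomised, give the evaluable number as a range below 500 (as few as about 312 at the loss Section 3.9 allowed for), and acknowledge the correspondingly wider interval. The lower end should be labelled as a worst case, not an expectation.

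Either route costs wording only. The second also means stating a less favourable precision than 500 evaluable participants would give.

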#### **2** Background

### 2.1 The global burden of preventable diseases

Preventable diseases are a leading cause of ill health, contributing to a decrease in quality of life for individuals suffering from these conditions. Cardiovascular disease, type 2 diabetes and musculoskeletal disorders alone contribute to an estimated 5.5 Million years lost to these conditions (Disability Adjusted Life Years, DALYs) in the UK alone (James et al., 2008), and mental health conditions such as stress, anxiety and depression are estimated to affect 1 in 4 people at some point in their lives. The chronic disease burden affects individuals from all ages, socio-economic conditions and professions.

In addition to these chronic diseases, the COVID-19 pandemic has had a significant impact in the wellbeing and mental health of Britons (Fancourt et al., 2020, Office for National Statistics, 2020). A recent survey shows that 79% of responders report lower levels of quality of life and increased levels of anxiety and psychological distress compared to a similar period in 2019 (Fujiwara et al., 2020).

It is widely acknowledged that health and wellbeing of NHS staff is adversely affected by the high-risk workplace environment, with high prevalence of mental health (anxiety and depression) conditions (NHS staff survey, 2019). 58% of frontline and social care workers meet the criteria for having significant anxiety, depression and PTSD. NHS staff have reported SAD to be the primary reason for absenteeism (~21%), totalling 472,426 days lost in that month alone.

Levels of psychological distress have further increased during COVID-19 with the added pressure on the healthcare system in dealing with increased hospitalization rates, increased hospital mortality rates and fears of infection from working in locations with high risk of exposure to the virus and concerns regarding the provision of personalised protective equipment (Kisely et al., 2020; Holmes et al., 2020).

### 2.2 Lifestyle changes and their impact on Quality of Life

The observed continuous increase of the burden of preventable chronic diseases across the globe indicates that current strategies, which have mainly focused on treatment after the fact, have not been effective in tackling the prevention component of this issue adequately. Healthcare treatment is estimated to contribute to only 10% of premature deaths in the United States, while behavioural patterns such as tobacco smoking and dietary habits contributing to around 40% (Schroeder, 2007). Thus, while improving health care systems is important, switching the paradigm with a focus on prevention by improving behavioural choices, rather than treatments, is of crucial importance.

The burden of preventable chronic diseases can be reduced, by adherence to lifestyles that reduce the known risk factors. To the individual, lifestyle changes have the potential to increase their quality of life with the downstream potential of delaying or averting preventable diseases (Eriksson et al., 2006, 2010, Toobert et al., 2003).

Likewise, a focus on health as multidimensional construct that joins objective measures of health such as causes of death and life expectancy with more subjective measures of wellbeing (emotional, social, environmental, etc.), commonly referred to as Quality of Life (QOL), is essential to tackle the health burden across the world (Audureau et al., 2013, Kyu et al., 2018).

Quality of life (QoL) is a measure of perceived quality of an individual's daily life, incorporating their perspective of physical, mental, and social well-being in the context of the culture and value systems in which the individual lives and in relation to their goals, expectations, standards and concerns (World Health Organization, 1995).

Title: Pilot	Title: Pilot evaluation of a personalised, prevention mHealth partner, SYD, and its impact on Quality of Life of NHS staff								
Authors	[name], [name], [name], [name], [name]	Ver.	2.0	Date Authorised	13/04/2022	Page 7 of 24			

QoL is closely related to physical and mental health, as individuals living with conditions such as obesity (Sach et al., 2007), diabetes, cardiovascular risk factors (Sullivan et al., 2007), anxiety (Olatunji et al., 2007), stress (de Frias et al., 2015) and depression (Ruo et al., 2003), consistently report lower levels of QOL. Lifestyle interventions such as supervised exercise training (Eriksson et al., 2010) or personalised counselling (Lindström et al., 2006), have shown success in increasing and sustaining individual's QOL in the long run, however, these interventions frequently report reduced effectiveness due to poor attendance and adherence rates.

Several factors have been identified to predict lower adherence to lifestyle interventions, including unrealistic expectations, lower baseline mood or gaps in knowledge (Burgess et al., 2017). Indeed, behavioural treatment strategies such as self-monitoring (Mahoney et al., 1973), self-reinforcement and goal-setting with specific, measurable, attainable, realistic and time-framed goals (Bovend'Eerdt et al., 2009), have been shown to be some of the most important drivers in improving adherence to lifestyle modifications with behavioural change most likely to be achieved when it is self-motivated, personalised to each individual and rooted in positive thinking (World Health Organization, 2003).

To tackle these issues, mobile health (mHealth) interventions can provide a solution to increase individual's adherence to health and wellbeing recommendations (Vlahu-Gjorgievska et al., 2018). The widespread use of smartphones, as well as integration with other health-oriented devices, such as fitness trackers, allows for recommendations to be personalised based on each individual's lifestyle patterns, personality, environment, personal choices and goals. In turn, individuals are more likely to be engaged with their own progression towards significant behavioural changes, with the ultimate goal to increase their quality of life over the long term.

### 2.3 SYD – a personalised preventative mHealth partner for everyone

iamYiam has developed a platform and a mobile app named SYD, that use an AI-powered predictive engine to give recommendations for personalised preventative actions to users, with the goal to improve the quality of life. Its main focus is to support the prevention of lifestyle-related conditions in a non-invasive and non-clinical intervention that empowers individuals to take control of their own wellbeing through small meaningful and personalised steps.

SYD tracks each individual's health and wellbeing through 300+ variables mapped to 9 high-order dimensions (hereby referred to as Life Quality Indices, LQIs) based on Stanford's Well for Life dimensions of well-being (Heaney et al., 2017): physical health, emotional health, financial health, purpose, social life, brain power, self-esteem, environment, and career.

SYD incorporates published models and validated scales to quantify each individual's risk of cardiovascular disease (CVD), risk of developing type 2 diabetes, level of musculoskeletal disorders (MSK) such as back and neck pain, as well as levels of stress, anxiety and depression, providing each individual with a detailed assessment of their physical and mental health risks.

An internal (unpublished) assessment of iamYiam's active users of SYD over a period of 19 months amongst 350 users, has shown an increase on all LQIs, averaging at 30% across all dimensions and reaching as high as +61% (self-esteem).

These 300+ variables are generally presented to the individual in the form of questions, many of which are extracted from validated questionnaires/surveys or indices, such as the National Health Interview Survey (NHIS), the Pittsburgh Sleep Quality Index (PSQI), the Patient Health Questionnaire (PHQ-9) or the UK Biobank.

The user can answer these questions throughout their journey and interaction with SYD, which is mediated through a conversational agent that creates a bridge between the user and the content on the iamYiam platform, while keeping the interaction fun and engaging. SYD uses natural language understanding and generation to predict the context of

Title: Pilot evaluation of a personalised, prevention mHealth partner, SYD, and its impact on Quality of Life of NHS staff							
Authors	[name], [name], [name], [name], [name]	Ver.	2.0	Date Authorised	13/04/2022	Page 8 of 24	

the conversation and user intents, providing relevant and useful information in an intuitive way. It also appreciates context – as an example, vegetarians are not presented options for supplements derived from fish or meat.

### 2.4 SYD's evidence-based personalised lifestyle recommendation model

Our research evidence framework employs a strict assessment of the scientific evidence for each actionable recommendation within SYD, accounting to an evidence base of >2,500 meta-analyses and systematic reviews evaluating results of >10,000 research papers. Peer-reviewed articles are automatically fetched, scored and prioritised based on article-level metrics (normalised citation-based and altmetrics). These are analysed and curated by a team of expert scientists to validate and extract relevant features such as effect and population sizes, inclusion/exclusion criteria and demographics of the groups. Evidence for effect of lifestyle interventions on a given health dimension are then aggregated and normalised effect sizes are used to estimate the change attributed to an individual performing a recommended action. These are normalised to account for the frequency and amount that individuals perform the recommended action, which is estimated by feedback and scheduling through the SYD app. To estimate the current health states of the individual, SYD uses AI state estimation models (multidimensional Kalman filters) accounting previous state estimations, covariance between states and uncertainty through time.

By analysing each individual's past behaviour and preferences, and using aggregated data from similar users, SYD's recommender system predicts and presents lifestyle recommendations for which the individual is more likely to be interested and act on, and which are expected to have the most significant impact on their wellbeing. Each recommendation is presented in a succinct manner while providing information of the scientific evidence (references and abstract links and a simplified summary of that evidence), driving those recommendations. Information on which LQIs are expected to be affected and the estimated mean effect and timeframe of those changes are also shown. By interacting with SYD and performing recommendations, the user can track their progress through each LQI in an intuitive way (with training to enable this), allowing them to observe the effect of behavioural changes through time.

To ensure that SYD adapts to each individual as they journey life, it provides the user with the ability to give feedback on any aspects of the platform including recommendations, goals, and conversations with SYD and on the app design itself. This allows SYD to evolve locally in line with user feedback, as well as more widely by prompting iamYiam to adapt to insights on what needs to change for its users to increase and/or maintain their engagement to enabling healthier lifestyle choices in the long run.

With this study, we aim to provide NHS healthcare staff with SYD, a research based, conversational wellbeing companion, to see if this will positively impact their quality of life, given that they are amongst those most likely to require support, particularly during COVID-19 pandemic and aftermath.

